Functional Performance was measured using the Medical Outcomes Short-Form-36 (SF-36)¹¹² pre-/post-surgery and after wks 3 & 6. SF-36 uses norm-based scoring with physical and mental health components of the SF-36 scored to have the same mean (50) and SD (10) in the general U.S. population, with component scores ranging from 20 to 70. The Mental Health component of the IG (Fig 7) consistently improved from a mean pre-surgery level of 48.2 to 57.5 at wk 6 (exceeding national norm of 50). Conversely, the UCG's mean Mental Health component scores *dropped* after surgery and stayed relatively flat for wks 3 & 6 (47.4 and 47 respectively). Physical Health component scores dropped for both groups post-surgery, with IG's improving from post-surgery 30.2 to a wk 6 of 45.2. The UCG improved at a much slower rate, starting at post-surgery level of 32.7 and improving to 38.8 at wk 6 post-study.

[figure not shown]

Figure 6. Other Symptom Mean Scores (Number, Severity, Interference) (0-10. 10 = Most Severe and Most Interference)

Implications of Preliminary Work. Results justify efficacy testing with a larger sample, attention control group, and focus on optimal timing and sustainability of the exercise intervention. The proposed intervention retains all pilot components, incorporating participant feedback to add exercise flexibility with/without the Wii after achieving 10 mins/day of continuous walking for 5 days/wk.

Section 3.0 Eligibility Criteria

The research proposed for this application is a randomized controlled trial (RCT) to determine the efficacy, optimal timing, and sustainability of an innovative home-based exercise intervention for post-surgical non-small cell lung cancer (NSCLC) patients after discharge from the hospital. This exercise intervention is designed to enhance perceived self-efficacy (PSE) for cancer-related fatigue (CRF) self-management to improve CRF severity and fatigability (fatigue associated with activity, an indicator of functional capacity) to augment the rehabilitation of persons of all ages with NSCLC after surgery.

No special vulnerable populations will be studied.

Eligibility. Based on results of our R21 RCT, we will use criteria shown for participation in this study:

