5C1a) The exercise intervention is designed to promote regular, light-intensity walking and balance exercise < 3.0 metabolic equivalents (METs), which corresponds to usual activities of daily living.¹¹⁸ Combining walking with balance exercises has been found to have a positive effect on balance, and walking confidence and speed.^{119,120} Participants will perform warm-up exercises designed for this patient population. Walking should be comfortable and self-paced (e.g., they can stop instantly at any time unlike a treadmill). The Wii Fit Plus provides a virtual environment where the participant sees themselves, friends, and even their dog walking on a sunny day next to a stream, through a village with happy, familiar faces offering encouragement. As they walk in place in their home, they will see themselves taking a corresponding step in the virtual environment. We followed the American College of Sports Medicine (ACSM),^{37,80,82,121} American Heart Association (AHA),¹²² and American Cancer Society (ACS)^{79,83} principles of exercise prescription for duration (6 wks) and dosage (5 min increase per wk) for safe exercise prescription. Duration of walking will start at 5 mins/day, 5 days during wk 1, and will build by 5 mins/day each week with the goal of walking 30 mins per day during wk 6 (Appendix A1). Increase in walking duration will be assessed by the exercise nurse intervener at the start of each week. Duration will be increased 5 mins each week if participant's PSE for attaining that duration is $\geq 70\%$ on a 0-100% scale (100% = high PSE).¹²¹ Gradually increasing walking duration promotes achievement of exercise goals, building PSE for CRF self-management and walking. Incorporating feedback from our R21 RCT, participants who can achieve a minimum of 10 mins continuous walking will be given the option to use the Wii or walk outside or at a place of their choice (mall, gym) to achieve their walking prescription. Participants will also perform Wii Fit-Plus balance exercises 5 days/wk for wks 1-6 (Appendix A1). Participants will self-select from a menu of predetermined Wii balance exercises, with each exercise taking less than 3 mins to complete. Balance exercises use a gaming format and scoring systems as motivation to improve performance. Exercises include downhill skiing, soccer, golf, and video game activities. Exercises use competitive and engaging formats, keeping users captivated so they forget they are exercising. Exercises provide encouragement that participants can partake in hobbies in which they may have thought they could never participate again. Participants will wear a pedometer to record their total steps/day. Pedometers will not be worn during exercise so non-intervention activity can be compared with the activity of the ACG and wks 1-6 of the WCG. Data are recorded in participant's Daily Diary (Appendix A2). IIG participants receive the exercise intervention during wks 1-12 post-surgery and WCG participants will receive usual care, which is standard medical care from health providers for 6 wks after hospital discharge followed by the exercise intervention during wks 7-12. Safety: Inclusion criteria require that participants have phone access while exercising, should participant need assistance. Participants are provided safety criteria in the Daily Diary prior to start of each exercise intervention. Participants are taught to maintain a light-intensity dose of exercise by: 1) using portable pulse oximeter to ensure heart rate $\leq 60\%$ of heart rate reserve;^{37,80} 2) ensuring perceived level of exertion is <3 on a scale of 0-10;^{37,79,80} and 3) ensuring they can talk and sing while exercising (Talk Test).^{37,80,121,123} Participants will document any symptoms/problems that occur during exercise intervention and any action taken in Daily Diary, for review by nurse. Nurse will be available by phone and can make a home visit to ensure participant safety. Note that no safety issues were reported in either the single-arm or the R21 RCT.

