Perceived Self-Efficacy	CRF and Walking Self-management	PSE for Fatigue Self-Management (6 items), Walking Duration (12 items)	Pre & Post-Surgery Weeks 1-12	PSE for CRF self-management (.92) and PSE for walking duration (.95).
Perceived Self-Efficacy	Balance	Activities-specific Balance Confidence (16 items)	Pre & Post-Surgery Weeks 3, 6, 9, 12	PSE for balance for increasingly challenging activities (.82-.90).
CRF Self-Management Behaviors	Walking Exercise	Recorded in Daily Diary and electronically in the Wii Fit Plus	Weeks 1-12	Total number of minutes walked with the Wii per week.
CRF Self-Management Behaviors	Balance Exercise	Recorded in Daily Diary and electronically in the Wii Fit Plus	Weeks 1-12	Total number of balance exercises completed with the Wii per week.
Functional Status	Capacity	Fatigability; Six-minute Walk Test	Pre-Surgery, Prior to Chemo/Week 6, & 12	Degree of fatigue associated with walking during the six-minute walk test. Distance walked in six minutes.
Functional Status	Performance	SF-36 v2 – 8 subscales accounting for two components, physical and mental health (36 items)	Pre & Post-Surgery Weeks 3, 6, 9, 12	Performance of daily mental and physical activities that people do in the normal course of their lives (.78-.92)
Functional Status	Performance	Pedometer Daily Diary	Weeks 1-12	Performance in average number of steps taken per day per week
Quality of Life	Quality of Life	QOL Index: Overall QOL, Family, Health/Function, Socioeconomic, Psych/Spiritual (66 items)	Pre & Post Surgery Weeks 3, 6, 9, 12	Satisfaction with various aspects of life and the importance of each aspect of life to the person (.73-.99)

Legend: Surgery = Sx; CRF = Cancer-Related Fatigue. PSE = Perceived Self-Efficacy. Medical Outcomes Short Form-36 v2 = SF-36 v2. QOL = Quality of Life

Revision 5/19/2019. Updated Table with the following 3 measures added.

Table 3. Main Concepts, Variable, Measures, Collection Schedule, and Measurement Objective

Concept	Variable	Measure # Items	Schedule	Measurement Description (Cronbach's alpha)
Symptoms	Sleep Impairment	PROMIS v 1.0 Sleep-Related Impairment Short-Form 8a (8 Items)	Pre & Post-Surgery Weeks 3, 6, 9, 12	Degree of sleep-related impairment. (0.90)
Symptoms	Pain Source, Pain Treatment, Severity and Interference Information	The Brief Pain Inventory (4 Severity Items; 7 Interference items; 4 Source Items)	Pre & Post-Surgery Weeks 3, 6, 9, 12	Degree of pain severity and impact of pain on every day. living. (0.77 to 0.91)

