Perceived Self-Efficacy	Pain Self-Management	The Perceived Self-Efficacy for Pain Self-Management Inventory (6 Items)	Pre & Post-Surgery Weeks 3, 6, 9, 12	Degree of pain self-management. (0.90)

Aim 2 – Measures – WCG Delayed Intervention. At the start of wk 7, WCG will begin the intervention, concluding at wk 12. Aim 1 study variables and measures (Table 3) will be analyzed for Aim 2 for wks 7-12 to compare with the IIG wks 1-6 outcomes.

Aim 3 – Measures – IIG Intervention Sustainability. At the start of wk 7, IIG participants will be given the option to extend the intervention an additional 6 wks. We will measure the extension rate as % participants who elect to extend. Adherence to the intervention will be measured as % participating in the intervention who adhered to prescribed intervention. Weekly adherence will be calculated by taking number of times prescribed intervention was completed divided by total number of interventions prescribed for week. These data are recorded in the Daily Diary and will be confirmed by research staff reviewing recorded data in Wii Fit-Plus. Retention, measured as part of sustainment, will be calculated as % who elected to extend 6 wks who completed final data collection at wk 12. Based on our conceptual definition of sustainability, we will measure the extent to which components of the intervention were rated acceptable for continued use by participant. Acceptability will be measured at end of wk 6 and 12 using a 15-item Acceptability Questionnaire (Appendix B1) using a numeric scale (1 to 6: 6 = agrees strongly) with higher scores indicating greater acceptability of the exercise program. The Questionnaire has a Flesch-Kinkaid 6th grade reading level and was successfully used in our R21 RCT and allows participants to rate how well barriers and facilitators to exercise are addressed. Open-ended questions provide further input.^{23,24} Efficacy will be measured using the same study variables and measures analyzed in Aim 1 (Table 3) for wks 7-12.

Section 8.0 Drug Formulation and Procurement

Not applicable. This study is not a pharmaceutical trial.

Section 9.0 Toxicity and Adverse Event Reporting Guidelines

Study Monitoring

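### Table 3 counts only walking done with the Wii, although the walking prescription may be met elsewhere, and no check is stated for sessions away from the Wii

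*Combined protocol and SAP*

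**What the plan says.** - **Section 7.0, Table 3, Walking Exercise row.** The data are "Recorded in Daily Diary and electronically in the Wii Fit Plus" in weeks 1-12, and the quantity to be derived is "Total number of minutes walked with the Wii per week".
- **Section 5C1a.** The exercise description says that "participants who can achieve a minimum of 10 mins continuous walking will be given the option to use the Wii or walk outside". Malls and gyms are named as further examples, and walking in any of these venues fulfils the prescription. The same section has the pedometer taken off during exercise.
- **Section 2N, Implications of Preliminary Work.** The option is new to this trial. Pilot feedback was used to "add exercise flexibility with/without the Wii after achieving 10 mins/day of continuous walking for 5 days/wk".
- **Section 7.0, Aim 3 measures.** Weekly adherence is the number of completed sessions over the number prescribed, taken from the Daily Diary. These data "will be confirmed by research staff reviewing recorded data in Wii Fit-Plus". No other check is named.
- **Section 7.0, secondary outcome measures.** The Daily Diary holds the weekly prescription and each day's performance. This description is not limited to the Wii.

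**The concern.** A Wii-only definition suits an intervention done entirely on the Wii. Here the intervention was widened and the Table 3 row does not reflect it. Read literally, the walking variable drops minutes that the protocol itself treats as delivered exercise. No other defined variable recovers them, since step counts exclude exercise by design.

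Two uses are exposed. First, Section 7.0 carries the Table 3 variables into Aim 2 (wait-list weeks 7-12 against immediate-group weeks 1-6) and Aim 3 (immediate-group weeks 7-12). If use of the off-Wii option differs between those periods, recorded walking would differ for that reason alone. Second, adherence above 70% is part of Hypothesis 3. The plan does not say what happens to a diary session with no matching Wii record.

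**Working it through.** **Inputs**

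- Section 5C1a: 5 min/day on 5 days in week 1, rising by 5 min/day each week to a goal of 30 min/day in week 6.
- Section 5C1a: the off-Wii option opens at 10 continuous minutes. Section 2N attaches 5 days a week to that threshold. The two wordings give different earliest switch points and need to be reconciled, so both are shown.
- Section 2N, pilot Aim 1 results: participants asked for another venue after 10 minutes on the Wii. This permits a narrower reading, with 10 minutes on the Wii and the rest elsewhere.
- Section 5C2: the goal in the extension period is at least 30 min/day.

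**Assumptions.** Full adherence, full weekly progression, and a Wii log that does not show walking done elsewhere. For weeks 7-12, 30 min/day on 5 days a week is assumed.

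**Step 1: reproduce the plan's figure.** Minutes per day in week w = 5w, so week 6 gives 5 × 6 = 30 min/day, as stated.

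**Step 2: prescribed minutes.** Weekly minutes = 5 days × 5w = 25, 50, 75, 100, 125, 150. The sum over weeks 1-6 is 525. Weeks 7-12 add 6 × 150 = 900, for 1,425 over 12 weeks.

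**Step 3: share captured by the Table 3 variable** (Wii minutes ÷ prescribed minutes)

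| Case | Weeks 1-6 | 12 weeks |
|---|---|---|
| A. All walking off the Wii from week 3 | (25 + 50)/525 = 75/525 = 14.3% | 75/1,425 = 5.3% |
| B. All walking off the Wii from week 2 | 25/525 = 4.8% | 25/1,425 = 1.8% |
| C. 10 min/day kept on the Wii, rest elsewhere | (25 + 5 × 50)/525 = 275/525 = 52.4% | (275 + 300)/1,425 = 40.4% |

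In case A the variable is 0 of 450 minutes in weeks 3-6. In case C it falls to 50/150 = 33% in week 6. In weeks 7-12, cases A and B record no walking at all.

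**Step 4: adherence.** Under the stated ratio from the diary, walking adherence is 5/5 = 100% every week in all three cases. If staff accepted only walking sessions with a Wii record, case A would give 2 weeks × 5 = 10 of 6 × 5 = 30 sessions, or 33%, over weeks 1-6.

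**The case against.** The strongest reply is that this is one loosely worded table cell. The diary is a named source for the variable and records daily performance. Nurses review it at visits, and Section 5C3 uses it weekly to judge whether the prescription was carried out. Balance exercises stay on the Wii and are counted separately. All of that stands. A reader might infer that an outdoor walker is recorded as having done almost nothing, but the documents support this only for the single Table 3 variable.

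A reader might also infer that adherence and the per-protocol set are understated. Adherence is a completed-over-prescribed ratio, and off-Wii walks meet the prescription, so they are completed sessions. The ratio falls only if Wii confirmation is made a condition, and no such rule is stated. Section 10.0 plans a per-protocol analysis without defining its set, and nothing ties it to Wii minutes.

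A third tempting inference is that the fittest participants choose to walk outdoors, so that a dose-response estimate is biased or even reversed. Nothing in the documents says who takes the option, and Section 10.0 lists no dose-response analysis. The threshold confines the undercount to those who reach 10 minutes, but that is only the week 2 prescription, so eligibility may be broad.

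The reply is also right that 14% is not the only plausible figure. Case C captures about half, and 525 minutes is the full-progression schedule, because each increase depends on the participant's self-efficacy rating. The diary form and exercise prescription are in appendices not available here, so an off-Wii field may already exist. None of this removes the mismatch: whatever the diary holds, Table 3 says to derive Wii minutes from it.

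**Conclusion.** The point holds in a limited form. The Table 3 definition contradicts the intervention described in Section 5C1a, and the only stated check on adherence is one that is assumed unable to see off-Wii walks.

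The variable would capture roughly 5% to 52% of prescribed minutes over weeks 1-6 for a fully adherent participant who uses the option. The figure depends on when the switch occurs and whether 10 minutes a day stay on the Wii. How many participants would use the option is not stated, so the average loss in a study group cannot be computed.

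The damage is confined to uses of the walking variable and to the confirmation of adherence. Brief Fatigue Inventory scores, fatigability, the sample size and the Section 10.0 models are untouched. It is worth correcting because the variable is carried into Aims 2 and 3 and the correction is cheap.

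**What to change.** - **Table 3, Walking Exercise row:** define the measure as total prescribed-walking minutes per week in any venue, taken from the Daily Diary, with Wii and non-Wii minutes recorded separately.
- **Section 7.0, Aim 3 measures:** score adherence on the diary total. State that the Wii log confirms only sessions recorded as Wii sessions, and that sessions elsewhere rest on the diary.
- **Daily Diary:** check whether it already has a field for off-Wii minutes, and add one if it does not.

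The exercise prescription does not change. The cost is a wording change and some diary coding. The downside is that off-Wii minutes are self-report only. Keeping the two kinds of minutes apart lets the analysis show how much of the recorded dose has device support.

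If diaries have already been collected without venue or off-Wii minutes, those minutes may not be recoverable. The report should then label the existing variable as Wii walking only, not as total walking dose.

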
Section 5.0 Research Design

5A) Introduction to the Research Design of Proposed Project

We propose a three-arm, repeated measures RCT for persons undergoing NSCLC surgery as shown in **Fig 8**. The design provides for **efficacy** comparisons of outcome measures among the immediate (exercise) intervention group (IIG), the wait-list control group (WCG) usual care, and the attention control group (ACG) by age after 6 wks (**Aim 1**) through the measurement of primary and secondary outcomes. The design also provides for evaluation of the timing of the intervention (**Aim 2**) by comparing study outcomes of the IIG's wks 1-6 with those of the WCG's wks 7-12 by age to account for time since surgery. Note that the timing of the data collection occurs near the time of the assessment during the week when the assessment is conducted. For example, if a participant has an unexpected visitor at their home and would like to have the data collector call the next day, then the data collector may call the next day. Unlike mice or non-human studies, we need to balance absolute timing against the needs of our human participants so we incorporate some flexibility required of our human participants when collecting data. Determining optimal timing to initiate an exercise program for post-surgical NSCLC patients is needed. We chose to start the WCG intervention at 6-wks post-hospital discharge based on Leach et al.'s¹¹³ findings that 43% of the 66 postsurgical NSCLC patients in their study preferred to start an exercise program during adjuvant treatment. Also, adjuvant treatment (radiation and/or chemotherapy) commonly begins 4-10 wks after surgery, with nearly 30% of patients undergoing adjuvant treatment¹¹⁴ Sustainability of the intervention (**Aim 3**) can be determined by offering the IIG the option to extend their exercise to 12 wks and calculating the percent that elect to extend, assessing acceptability, adherence, and retention while measuring primary and secondary outcomes for efficacy. Adverse events will be monitored to provide for safety (R21 RCT reported no adverse events).

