
5C2a) WCG participants will have baseline data collected pre-surgery by the nurse recruiter and receive a pedometer and instructions for recording total steps/day in Daily Diary (Appendix A7). The WCG nurse intervener (nurse) will visit in the hospital post-surgery to review study trajectory. Research staff will contact WCG by phone within approximately 24 hrs of discharge to collect post-surgery data (if too ill, data collection rescheduled within 3 days of discharge). Research staff will perform phone visits using protocol in Appendix A8 at the approximate end of wks 1-6 to control for staff interaction and data collection. During wk 6, an exercise nurse intervener will make a phone visit to screen participant’s readiness to start intervention as described for IIG participants. Once participant is ready to start, nurse will arrange home visit within approximately 3 days. The exercise intervention and procedures will be identical to those received by the IIG group during wks 1-6. Staff contact WCG by phone (if too ill, data collection re-scheduled within approximately 3 days) to collect data at the end of approximately wks 7-12.

5C2b) ACG participants will have baseline data collected pre-surgery by a nurse recruiter and receive a pedometer and instructions for recording total steps/day in Daily Diary (Appendix A7). The ACG nurse intervener will visit in the hospital post-surgery to review study trajectory, make a phone visit within approximately 4 days of post-surgical discharge to initiate the ACG intervention (Appendix A3), and make phone visits at the start of approximately wks 2-6. During visits, the nurse will deliver the ACG intervention. Data collectors will contact ACG by phone within approximately 24 hrs of hospital discharge (if too ill, re-scheduled within approximately 3 days of discharge) and at the approximate end of each week for 6 wks to

obtain outcome measures.

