Justification: To assess the certainty in performing pain-managing behaviors. The PSEPSM was used in the parent NIH, NCI R21 study that led to this current NIH, NCI R01 study. The PSEPSM Instrument is a self-report measure containing 6 items related to the certainty in performing pain-managing behaviors that takes 3 minutes to complete. On an 11-point scale (0-10, 10 = very certain), respondents rate their certainty in performing pain-managing behaviors. For the duration of study participation, measurement will occur with participants pre-surgery, post-surgery, weeks 3, 6, 9, and 12. The PSEPSM has been psychometrically tested developed by the Principal Investigator, [name] [name], based on the Perceived Self-Efficacy for Fatigue Self-Management Tool with internal consistency of 0.92 in the surgical lung cancer population. A copy of the tool is provided in this revision.

Note: In Table 3, a schedule is provided for collection of data. All time points such as Pre- & Post-surgery and Weeks 1 – 12 are collected approximately at this time point.

Table 3. Main Concepts, Variable, Measures, Collection Schedule, and Measurement Objective

Concept	Variable	Measure (# of items)	Schedule	Measurement Description and (Cronbach's alpha):
Patient Characteristics	Physiological	Demographic Questionnaire; Medical Record; Karnofsky Performance Scale.	Pre & Post-Surgery Weeks 1-12	Pre-Surgery: Age; Sex; Race; Co-morbid Conditions; Smoking History; Body Mass Index (BMI); Medications. Post-Sx Treatments (walker, oxygen, adjuvant therapy); Functional Impairment. Post-Surgery: Stage of Cancer; Type of and Extent of Lung Resection; BMI; Medications; Post-Sx Treatments. Weeks 1-12: Medications; Post-Sx Treatment. Wk 6, 12: BMI.
Patient Characteristics	Contextual	Demographic Questionnaire	Pre-Surgery	Education Level; Employment Data; Health Insurance Status; Income Level; and Marital Status.
Symptoms	CRF Severity	Brief Fatigue Inventory (9 items)	Pre & Post-Surgery Weeks 1-12	Severity of CRF and impact of CRF on daily living (.82-.97).
Symptoms	Other Symptom Severity	M.D. Anderson Symptom Inventory Lung Cancer Module (22 items)	Pre & Post-Surgery Weeks 1-12	Severity of pain, nausea, disturbed sleep, distress, dyspnea, difficulty remembering, decreased appetite, drowsiness, dry mouth, fatigue, sadness, numbness/tingling, vomiting, sore throat, cough, constipation and impact on daily living (.82-.94).

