AEs will be collected from the time the subject signs the consent form until 30 days after the final protocol specified intervention. All AEs will be followed until resolution or a cause is identified. AEs judged by the investigator as not related or probably not related to the treatment will NOT be followed beyond the end of the study.

Section 10.0 Statistical Considerations

Statistical Analysis. All tests of hypotheses will be two-tailed at $\alpha=0.05$. We compare groups at baseline using parametric and non-parametric tests to assess equivalence of confounding physiological and contextual patient characteristics, and pre-surgical outcome variables. If substantive differences exist, they will be controlled for in subsequent analyses by regression techniques, guided by the degree of dissimilarity rather than strict statistical significance.¹⁴⁴

Primary analysis (Aim 1) is the comparison among study groups of the primary outcome CRF severity and fatigability assessed at approximately 6 wks post-surgery. Analysis is based on a regression model for both CRF scores with the following variables in the regression equation: baseline CRF, study group, age, and (if appropriate) plausible interaction between these variables. We test association of study group with outcomes.

In Aim 2 our hypothesis comparing outcomes in IIG and WCG by age group will be addressed in the context of a longitudinal analysis. There are 6 time-ordered differences between IIG and WCG. We use generalized linear (mixed) models to allow flexible correlation structures in the repeated measures.^{145,146} Our regression equation has in addition to the aforementioned variables: time (week) of assessment, and critically, study group with time interactions. The model allows us to test if group effects are changing over time – referred to as a “parallel” profile analysis.¹⁴⁷ If the hypothesis is supported, we test whether that average profiles (over time) in

the two groups are the same. Aim 3 concerns three binary responses in the IIG group at 6 wks: extension, retention, and adherence. Logistic regression models will be used to assess the influence of explanatory variables on the likelihood of outcome.¹⁴⁷⁻¹⁴⁹

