Secondary Outcomes: An analogous strategy is applicable to continuous outcomes assessed at 12 wks. We will use linear models with the caveat that models are conditional on electing to extend participation. Statistical analysis will include intent-to-treat (ITT) analysis and per protocol analysis.^{150,151} ITT principle calls for making inference on the whole sample, with patients as randomized to their study group.¹⁵² To address missingness in our response data we will explore strategies for imputation.¹⁵³ The techniques described above allow missing at random (MAR). Inverse-probability weighting¹⁵⁴ will be investigated to accommodate missing data patterns that are not MAR. Assurance of analysis robustness and minimization of bias: We use a range of outcome measures based on the patient-centered principle to ensure the relevance of the study both biologically and practically. To enhance reproducibility, we will ensure protocol fidelity and follow our analytic plans, including addressing missing data in outcomes. To minimize analysis bias, we will adjust for factors such as potential between group unbalance and examine the robustness of our conclusions under deviations of model assumptions.

Note: Determination of Sample Size is discussed under the Research Design (Section 5, specifically, Section 5B)

TIMELINE. The research timeline is shown in Table 4.

POTENTIAL PROBLEMS AND ALTERNATIVE STRATEGIES. We acknowledge that NSCLC patients after surgery may be subject to complications requiring a break from the intervention. Should participants report unmanaged symptoms or clinical problems, they will be referred to their health care provider per protocol. Should the participant become ill, causing them to miss three consecutive exercise interventions, the participant will be instructed to call their nurse, who will reevaluate and adjust the exercise prescription per protocol. Should the primary nurse intervener become ill or unable to meet with participant, a pre-assigned secondary nurse intervener will step in. There could be diffusion of treatment effects between IIG, WCG, and ACG as well as confounding effects if a disproportionate number of physically active participants are assigned to the IIG, WCG, or ACG. We will assess functional capacity levels and use block randomization to minimize these effects.

Table 4. Research Timeline	Year 1				Year 2				Year 3				Year 4				Year 5			
Activities	Q1	Q2	Q3	Q4																

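### As listed, the Aim 2 model omits the wait-list arm's weeks 1-6 scores, so wait-list patients lost before week 7 contribute no outcome data, and no committed method brings them back

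*Combined protocol and SAP*

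**What the plan says.** **Which weeks enter.** Three places agree. Section 7.0 (Aim 2 measures) says the study variables "will be analyzed for Aim 2 for wks 7-12 to compare with the IIG wks 1-6 outcomes". Section 5A describes "comparing study outcomes of the IIG's wks 1-6 with those of the WCG's wks 7-12 by age to account for time since surgery". Section 10.0 adds "There are 6 time-ordered differences between IIG and WCG", which leaves room for six WCG weeks only.

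**Which model.** Section 10.0: "We use generalized linear (mixed) models to allow flexible correlation structures in the repeated measures". The regressors are those of Aim 1, "baseline CRF, study group, age, and (if appropriate) plausible interaction between these variables", plus week and group-by-week. No WCG score from weeks 1-6 is listed.

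**What is recorded.** Section 5C2a: "Research staff will perform phone visits using protocol in Appendix A8 at the approximate end of wks 1-6". Table 3 schedules the Brief Fatigue Inventory at "Pre & Post-Surgery Weeks 1-12". The usual-care scores of the WCG should therefore exist.

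**Analysis population and missing data.** Section 10.0: "ITT principle calls for making inference on the whole sample, with patients as randomized to their study group". The same paragraph says that imputation strategies will be explored, that the techniques allow data missing at random (MAR), and that inverse-probability weighting will be investigated for patterns that are not MAR. None of this is tied to Aim 2, and no method or variable is named.

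**The concern.** The two arms enter Aim 2 at different distances from randomisation. IIG rows begin at discharge. WCG rows begin six weeks later, so they exist only for patients still in follow-up at week 7. Someone lost at week 4 contributes rows if randomised to IIG and none if randomised to WCG, although both have been scored weekly. Read literally, the model compares everyone who began follow-up in IIG with a WCG group selected after randomisation.

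The general MAR statement does not repair this. A likelihood-based mixed model protects against loss that depends on data inside the model. Here the scores most likely to predict early WCG loss are outside it, and only baseline fatigue and age stand in for them.

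At stake is Hypothesis 2, that immediate exercise improves outcomes faster and further than delayed exercise. Aim 2 sets exercise against exercise and the plan states no expected difference. The 1.8 to 2.2 point gaps that Table 1 implies for Aim 1 therefore give no reassurance that a bias of a few tenths is negligible.

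**Working it through.** **1. The plan's own figures.** No sample size, power or attrition is given for Aim 2. The Section 5B recruitment figures reproduce: 180/0.8 = 225, and 225/(0.9 × 0.9) = 277.8, or 279 when rounded up by arm (75/0.81 = 92.6, so 93 × 3 = 279). With 93 randomised to WCG, 20% attrition is 18.6, about 19 patients. The plan does not split this by arm or period. The pilot (Section 2N) retained 97% to week 6. A 3% loss would be 93 × 0.03 = 2.8, about 3 patients.

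**2. Assumptions.** From Section 5B: SD 2.0. Mine, because the documents do not give them: correlation r = 0.4 to 0.6 between any two weekly scores of a patient; correlation 0.3 with baseline; odds ratio of loss 2 to 4 per SD of the patient's weeks 1-6 mean.

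**3. Formula.** A six-week mean has variance 4v, with v = (1 + 5r)/6. Let a share d be lost before week 7, with a weeks 1-6 mean G points above that of the patients kept. The kept patients' weeks 1-6 mean is then d × G below that of all randomised WCG patients. Carrying this to weeks 7-12 uses slope r/v. Baseline adjustment removes 0.3 × 0.3/v of it. So

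bias = d × G × (r − 0.09)/v

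- r = 0.4: v = 0.500, factor 0.31/0.500 = 0.62
- r = 0.6: v = 0.667, factor 0.51/0.667 = 0.765

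**4. Results.** G comes from simulating the logistic dropout model. The low end takes r = 0.4 and odds ratio 2; the high end takes r = 0.6 and odds ratio 4.

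| Loss before week 7 | Low end | High end | Simulated, baseline-adjusted |
|---|---|---|---|
| 3% | 0.03 × 0.97 × 0.62 = 0.018 | 0.03 × 2.07 × 0.765 = 0.048 | 0.02-0.05 |
| 10% | 0.10 × 0.94 × 0.62 = 0.058 | 0.10 × 1.89 × 0.765 = 0.145 | 0.06-0.15 |
| 20% | 0.20 × 0.91 × 0.62 = 0.113 | 0.20 × 1.77 × 0.765 = 0.271 | 0.11-0.28 |

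The WCG mean is too low by these amounts when the more fatigued leave, and too high by as much if the dependence is reversed. With the weeks 1-6 scores in the model the simulated bias is within 0.005 of zero. That is by construction, since loss was made to depend on those scores alone.

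**5. Against sampling error.** With 60 per arm, the standard error of the difference in six-week means before baseline adjustment is √(2 × 4v/60): 0.26 at r = 0.4 and 0.30 at r = 0.6. In standard errors, the bias is:

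- 3% loss: 0.02/0.26 = 0.08 to 0.05/0.30 = 0.17
- 10% loss: 0.06/0.26 = 0.23 to 0.15/0.30 = 0.50
- 20% loss: 0.11/0.26 = 0.42 to 0.28/0.30 = 0.93

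For a nominal two-sided 5% test of that mean difference with no true effect, P(|Z + shift| > 1.96) is about 5% at 3% loss, 6-8% at 10% and 7-15% at 20%. The planned profile test is more complex, so this is a guide to scale only.

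**The case against.** **Exclusion is inferred.** A reader might infer that the plan removes WCG patients lost before week 7. It never says so. Section 7.0 lists the weeks to be compared and does not define an analysis set, and the six differences may only name the contrasts of interest. Imputation or weights built on weeks 1-6 scores would bring these patients back. This stands as far as it goes: the omission belongs to the model as listed, and the plan's intention is open. But exploring and investigating commit to nothing, and weighting is mentioned only for patterns that are not MAR.

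**Direction.** A reader might also infer that the delayed arm will look better than it is. Nothing in the documents says who leaves. Recovered patients may lose interest, and the most fatigued may stay for the promised exercise. If the fatigued do leave, the bias works against Hypothesis 2 and is conservative for the study's claim. This stands.

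**Loss may be small.** The plan calls its 20% conservative, and the pilot lost 3% by week 6. Section 5C2a reschedules data collection for patients who are too ill, and does not make the weeks 7-12 calls conditional on starting exercise, so the week 6 readiness screen should not be read as a further exclusion. This also stands, and it limits the size. Related loss nevertheless remains plausible: Section 5A places the usual start of adjuvant treatment 4-10 weeks after surgery, in nearly 30% of patients, and Section 10.0 anticipates complications.

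**Conclusion.** The point holds as a gap between the listed Aim 2 model and the whole-sample ITT statement, with a better method available from data already scheduled. The documents do not support saying that MAR fails outright. It fails within the listed model only if loss depends on weeks 1-6 fatigue beyond what the listed covariates explain.

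The size is modest. It is negligible at pilot-level loss, and reaches up to about one standard error only if all planned attrition fell before week 7 and loss were strongly related to fatigue. The correlations and odds ratios behind this are assumptions. The issue is separate from the difference in time since surgery between the two windows, and would remain if recovery were flat.

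**What to change.** State in Section 10.0 that the Aim 2 set is all randomised IIG and WCG participants. For the weekly outcomes, fit IIG weeks 1-6 and WCG weeks 1-12 in one mixed model. Give WCG weeks 1-6 their own usual-care week means, use a covariance that links the two WCG periods, and estimate the six exercise-week contrasts from that model. Imputing or weighting weeks 7-12 from the recorded weeks 1-6 scores is an acceptable alternative if the method is named.

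Say also that:

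- the estimate assumes MAR given the weeks 1-6 scores;
- for patients lost early it stands for the scores expected had they stayed in the study, including some who never began exercise;
- it helps little for fatigability, because Table 3 schedules the walk test only pre-surgery, prior to chemotherapy/week 6, and at week 12.

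The cost is SAP wording and six more week means (more if they differ by age group). No new data are needed. A fully unstructured 12-week covariance would have 12 × 13/2 = 78 parameters against 6 × 7/2 = 21 for six weeks, so a structured form should be named for about 60 patients per arm.
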